Verorab Rabies Vaccine: One dose consists of the administration of 0.5 mL of vaccine via the intramuscular route and contains

rabies virus, WISTAR Rabies PM/WI38 1503-3M strain

 $(inactivated) \ge 2.5 \text{ IU}.$

Subject Sample Size: N=80 (n=60 Pfs230D1-EPA/Matrix-M; n=20 rabies control)

Accrual Ceiling: N=150

Accrual Period: September 2021-October 2021

Study Duration: Start Date: approximately September 2021

End Date: approximately June2023 (includes data analysis)

Study participants will be enrolled for a total of approximately 14 to 16 months depending upon timing of screening

Study Population:

Healthy male and female adults (18 to 50 years of age) who reside in Sotuba and surrounding villages, Mali

Study Design:

This is a Phase 1, dose-escalating, randomized, double-blind, comparator-controlled study to assess the safety, tolerability, immunogenicity and transmission-blocking activity (TBA) of a 3-dose regimen of Pfs230D1-EPA/Matrix-M versus rabies vaccine in healthy adults. This will be a first-in-human assessment of Pfs230D1-EPA/Matrix-M. Participants will be randomized to one of the study arms. Participants will be followed for 12 months from the last dose of study vaccine for safety and tolerability, as well as immunogenicity and functional antibody responses.

The study groups and arms are as follows. For all participants, the assigned study vaccine will be administered at Days 1, 29, and 57.

Group 1: Pilot Group

- **Arm 1a** (n=5): 12.5 μg Pfs230D1-EPA/25 μg Matrix-M
- **Arm 1b** (n=5): 20 μg Pfs230D1-EPA/50 μg Matrix-M
- **Arm 1c** (n=5): 40 μg Pfs230D1-EPA/50 μg Matrix-M
- Arm 1d (n=4): rabies vaccine (standard dose)

Group 2: Main Group

- Arm 2a (n=15): 12.5 μg Pfs230D1-EPA/25 μg Matrix-M
- Arm 2b (n=15): 20 μg Pfs230D1-EPA/50 μg Matrix-M
- Arm 2c (n=15): 40 μg Pfs230D1-EPA/50 μg Matrix-M
- Arm 2d (n=16): rabies vaccine (standard dose)

Study Objectives:

Primary Objective:

• To assess in African adults the safety and the reactogenicity of administration of Pfs230D1-EPA/Matrix-M (first-in-human) as compared to the rabies vaccine control

Secondary Objectives:

- To assess level of and duration of humoral immune responses as measured by enzyme-linked immunosorbent assay (ELISA) titer response to Pfs230D1M after third immunization
- To assess the functional antibody response by standard membrane feeding assay (SMFA) to Pfs230D1M

Exploratory Objectives:

- To explore cellular and humoral responses to Pfs230D1M

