12.3 Investigator Assessment of Adverse Events

If a diagnosis is clinically evident (or subsequently determined), the diagnosis rather than the individual signs and symptoms or lab abnormalities will be recorded as the AE.

All solicited (see Table 9 below) and unsolicited AEs will be recorded through 7 days after each vaccination, including injection site reactions, or until resolved. After that period, only unsolicited AEs (including symptomatic malaria), SAEs, UPs, and NOCIs will be recorded. Note that a positive BS without associated clinical symptoms (i.e., asymptomatic parasitemia) will not be reported as an AE. Clinical or symptomatic malaria will be reported as an AE.

Table 9. Solicited Adverse Events

Systemic adverse events
Fever (temperature ≥38.0 °C)
Headache
Nausea/Vomiting
Diarrhea
Abdominal pain
Fatigue
Malaise
Myalgia
Arthralgia
Urticaria
Local reactogenicity
Injection pain/tenderness
Injection erythema/redness
Injection swelling
Injection induration
Injection pruritus
Limitation of arm movement
Limitation of arm movement

Abbreviations: ALT, alanine transaminase; ANC, absolute neutrophil count; AGC, absolute granulocyte count; CR, creatinine; WBC, white blood cell.

Additional laboratory abnormalities other than those specified as safety labs in the protocol should be reported as AEs if they require intervention. Interventions include, but are not limited to, discontinuation of treatment, dose reduction/delay, additional assessments, or concomitant treatment. In addition, any medically important laboratory abnormality may be reported as an AE at the discretion of the investigator. This could include a laboratory result for which there is no intervention, but the abnormal value suggests a disease or organ toxicity. In addition, , all laboratory AEs will be collected and graded through 14 days after the first and second vaccination and 28 days after the third vaccination or until resolved.

The investigator will assess all AEs with respect to seriousness (criteria listed above), severity (intensity or grade), and causality (relationship to study agent and relationship to research) according to the following guidelines.

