⁽¹⁾ Visit windows are based off timing of days post the preceding vaccination; (2) A complete physical exam will be performed at the screening visit. (3) Blood draw amounts are "up to" the mL listed for each laboratory. If less than that amount is collected, it will not be considered a deviation. (4) As per FDA guidelines, study days are listed with Day of Immunization #1 and Day 1 (rather than Day 0). Note that the study visits scheduled for Study Days 281, 337 and 393 may be conducted as phone calls if the participant is not able to come to the study site in person. * Hemoglobin typing will be done at the Day - 7 visit.

Day to Day Schedule

Study Day -7 (±7 days; Drug Treatment Visit)

- 1. Perform basic history and focused physical examination, emphasizing examination of any acute complaints.
- 1. Record vital signs (blood pressure, temperature, and heart rate).
- 2. Record AEs and concomitant medications, if applicable.
- 3. Obtain approximately 56 mL of blood for CBC with differential and platelet count, ALT, creatinine, malaria blood smear and PCR, hemoglobin typing, anti-Pfs230 antibody ELISA, standard membrane feeding assay (SMFA), cellular assays, transcriptional analysis.
 - If safety labs were obtained for screening within ≤ 2 days prior to day -7, can use for study day -7 visit and do not need to repeat.
- 4. For females, obtain a urine or serum sample for β-hCG testing. Ensure that the test is negative before proceeding.
- 5. For females, ensure agreement and compliance with pregnancy prevention before AL dosing.

Study Day 1 (±0 days; day of Vaccination #1)

The following evaluations/procedures will be completed before vaccination:

- 1. Ensure that all inclusion/exclusion criteria are met.
- 2. Ensure that CBC, ALT, creatinine, HIV, and urine results from screening are within protocol-defined limits (see Exclusion Criteria above) before vaccinating
- 3. Perform basic history and focused physical examination, emphasizing examination of any acute complaints.
- 4. Record vital signs (blood pressure, temperature, and heart rate).
- 5. During the physical examination, study staff will educate the subject regarding signs and symptoms of potential adverse events (AEs) and indications for use of antipyretics if fever, headache, or malaise occurs.
- 6. For females, obtain a urine or serum sample for β-hCG testing. Ensure that the test is negative before vaccinating.

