- 1. Perform basic history and focused physical examination (including injection site), emphasizing examination of any acute complaints.
- 2. Record vital signs (blood pressure, temperature, and heart rate).
- 3. Record AEs and concomitant medications, if applicable.

Study Day 43 (±3 days; 14 days after Vaccination #2)

- 1. Perform basic history and focused physical examination, emphasizing examination of any acute complaints.
- 2. Record vital signs (blood pressure, temperature, and heart rate).
- 3. Record AEs and concomitant medications, if applicable.
- 4. Obtain approximately 36.5 mL of blood for CBC with differential and platelet count, ALT, creatinine, malaria blood smear, anti-Pfs230 antibody ELISA, cellular and ex vivo assays, SMFA and transcriptional analysis.

Study Day 57 (±7 days; day of Vaccination #3)

- 1. Perform basic history and focused physical examination, emphasizing examination of any acute complaints.
- 2. Record vital signs (blood pressure, temperature, and heart rate).
- 3. Record AEs and concomitant medications, if applicable.
- 4. For females, ensure agreement and compliance with pregnancy prevention before vaccination

The following evaluations/procedures will be completed following vaccination:

- 1. Observe the subject for at least 30 minutes after vaccination to evaluate immediate adverse reactions.
- 2. Record vital signs (blood pressure, temperature, and heart rate).
- 3. Perform interim history and physical examination, focusing on any acute complaints.
- 4. Record AEs and concomitant medications, if applicable
- 5. Obtain approximately 16.5 mL of blood for CBC with differential and platelet count, ALT, creatinine, malaria blood smear, anti-Pfs230 anti body ELISA and transcriptional analysis.

Study Day 58 (±0 days; 1 day after Vaccination #3)

- 1. Perform basic history and focused physical examination (including injection site), emphasizing examination of any acute complaints.
- 2. Record vital signs (blood pressure, temperature, and heart rate).
- 3. Record AEs and concomitant medications, if applicable.

Study Day 60 (±1 day; 3 days after Vaccination #3)

- 1. Perform basic history and focused physical examination (including injection site), emphasizing examination of any acute complaints.
- 2. Record vital signs (blood pressure, temperature, and heart rate).
- 3. Record AEs and concomitant medications, if applicable.

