- 4. Obtain approximately 6 mL of blood for CBC with differential and platelet count, ALT, creatinine, malaria smear, and transcriptional analysis.

Study Day 64 (±2 day; 7 days after Vaccination #3)

- 1. Perform basic history and focused physical examination (including injection site), emphasizing examination of any acute complaints.
- 2. Record vital signs (blood pressure, temperature, and heart rate).
- 3. Record AEs and concomitant medications, if applicable.

Study Day 71 (±3 days; 14 days after Vaccination #3)

- 1. Perform basic history and focused physical examination (including injection site), emphasizing examination of any acute complaints.
- 2. Record vital signs (blood pressure, temperature, and heart rate).
- 3. Record AEs and concomitant medications, if applicable.
- 4. Obtain approximately 16.5 mL of blood for CBC with differential and platelet count, ALT, creatinine, malaria blood smear, anti-Pfs230 antibody ELISA, SMFA and transcriptional analysis.

Study Day 85 (±14 days; 28 days after Vaccination #3)

- 1. Perform basic history and focused physical examination, emphasizing examination of any acute complaints.
- 2. Record vital signs (blood pressure, temperature, and heart rate).
- 3. Record AEs and concomitant medications, if applicable
- 4. Obtain approximately 5.5 mL of blood for CBC with differential and platelet count, ALT, creatinine, and blood smear.

Study Day 113 (±14 days; 56 days after Vaccination #3)

- 1. Perform basic history and focused physical examination, emphasizing examination of any acute complaints.
- 2. Record vital signs (blood pressure, temperature, and heart rate).
- 3. Record AEs and concomitant medications, if applicable.
- 4. Obtain approximately 30.5 mL of blood for malaria blood smear and for cellular and ex-vivo assays.

Study Day 141 (±28 days; 84 days after Vaccination #3)

- 1. Perform basic history and focused physical examination, emphasizing examination of any acute complaints.
- 2. Record vital signs (blood pressure, temperature, and heart rate).
- 3. Record AEs and concomitant medications, if applicable.
- 4. For females, obtain a urine or serum sample for β-hCG testing. Ensure that the test is negative before proceeding.
- 5. Obtain approximately 11.5 mL of blood for malaria blood smear, anti-Pfs230 antibody ELISA, standard membrane feeding assay (SMFA) and transcriptional analysis.

Study Day 225 (±28 days; 168 days after Vaccination #3)

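### After dose 3 the last safety labs may be drawn as early as day 14 of a 28-day collection period, and antibody samples with ±28-day windows are analysed without their actual sampling day, although duration is an objective

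*Combined protocol and SAP*

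**What the plan says.** Appendix A counts each window from the dose before it: "Visit windows are based off timing of days post the preceding vaccination". The visits that matter here are headed "Study Day 71 (±3 days; 14 days after Vaccination #3", "Study Day 85 (±14 days; 28 days after Vaccination #3", "Study Day 113 (±14 days; 56 days after Vaccination #3" and "Study Day 141 (±28 days; 84 days after Vaccination #3". Study Days 225, 281, 337 and 393 also carry ±28 days.

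Blood count, ALT and creatinine are drawn at Days 71 and 85 and at no scheduled visit after that. ELISA and SMFA samples after dose 3 are drawn at Days 71, 141, 225, 337 and 393. Section 8.2 allows Days 281, 337 and 393 to be phone calls.

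Section 12.3 states that "all laboratory AEs will be collected and graded through 14 days after the first and second vaccination and 28 days after the third vaccination"; an event still open at that point is followed further. The first secondary objective (Synopsis and Section 4) begins "To assess level of and duration of humoral immune responses", and it refers to the ELISA response after the third immunization. For ELISA, Section 14.3.1 plans signed-rank tests within arm and the Wilcoxon-Mann-Whitney test. Section 14.3.2 plans the Wilcoxon-Mann-Whitney test for SMFA. Neither section mentions the actual sampling day, out-of-window samples or a measure of duration. Section 9.6.1 says only that kinetics after the third vaccination may be explored.

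**The concern.** There are two separate issues.

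The first is safety. Safety is the primary objective of this first-in-human trial, and Section 14.2 lists laboratory adverse events by vaccine allocation. If the last scheduled labs can be drawn well before day 28, the tables will describe a 28-day period that some participants were not tested through. After doses 1 and 2 the labs on the next vaccination day act as a backup. After dose 3 no scheduled visit does.

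The second is duration. Antibody is expected to fall after its peak. A value labelled only by visit then mixes true decline with the day on which the participant happened to attend. A rank test on such values compares arms, but it does not say how long the response lasts.

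**Working it through.** **Windows.** Dose 3 is at Study Day 57 ("Study Day 57 (±7 days; day of Vaccination #3"). Its own ±7 days does not widen the later windows, because those count from the actual dose. Days after dose 3 = Study Day − 57, plus or minus the tolerance. The nominal values reproduce those in Appendix A: 71 − 57 = 14, 85 − 57 = 28, 113 − 57 = 56, 141 − 57 = 84.

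| Study Day | Tolerance | Days after dose 3 | Samples relevant here |
|---|---|---|---|
| 71 | ±3 | 11–17 | safety labs, ELISA, SMFA |
| 85 | ±14 | 14–42 | safety labs (last) |
| 113 | ±14 | 42–70 | cellular and ex vivo only |
| 141 | ±28 | 56–112 | ELISA, SMFA |
| 225 | ±28 | 140–196 | ELISA, SMFA |
| 281 | ±28 | 196–252 | none |
| 337 | ±28 | 252–308 | ELISA, SMFA |
| 393 | ±28 | 308–364 | ELISA, SMFA |

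**Laboratory coverage.** The Day 85 visit has 42 − 14 + 1 = 29 permitted days, and 14 of them (days 14 to 27) come before day 28. At the extreme, the visit is on day 14 and the Day 71 visit is no later than that. Then 28 − 14 = 14 days of the stated period have no scheduled lab during them or after them. A Day 85 draw on days 29 to 42 may also leave days 15–28 without a draw, but it would still catch an abnormality that persisted. After doses 1 and 2 the 14-day labs may fall on day 11, but the next vaccination-day labs follow at 28 ± 7 = 21 to 35 days.

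**Antibody timing.** The Day 141 window is 112 − 56 = 56 days wide. The documents give no half-life, so h below is an assumption. With first-order decay, the ratio between the window edges is 2^(56/h). If sampling days are spread evenly over the window, the added SD in natural-log units is (56/√12) × ln 2 / h. Section 14.3.1 gives an SD of 0.887 for vaccinees three months after dose 2. The scale is natural log: exp(5.356736 − 3.688401) = 5.30, close to the stated 5.31-fold. The combined SD is √(0.887² + added²).

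| Assumed h (days) | Edge-to-edge ratio | Added SD | Combined SD | Rise in SD |
|---|---|---|---|---|
| 30 | 3.65 | 0.374 | 0.962 | 8.5% |
| 60 | 1.91 | 0.187 | 0.906 | 2.2% |
| 90 | 1.54 | 0.125 | 0.896 | 1.0% |
| 120 | 1.38 | 0.093 | 0.892 | 0.6% |
| 180 | 1.24 | 0.062 | 0.889 | 0.2% |

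**Effect on arm comparisons.** The 2.3-fold case in Section 14.3.1 was re-simulated with 20 versus 20, SDs 0.55 and 0.88, the Wilcoxon-Mann-Whitney test and 3,000 runs. Timing spread was added to the vaccinated group only.

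| Timing spread | Power, two-sided 0.05 | Power, 0.05/3 |
|---|---|---|
| none | 0.913 | 0.816 |
| h = 30 | 0.880 | 0.758 |
| h = 60 | 0.915 | 0.786 |
| h = 120 | 0.921 | 0.798 |

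The first row agrees with the plan's claim of more than 80% at the 0.05 level. Simulation error is about √(0.91 × 0.09/3000) = 0.005 in the middle column and √(0.80 × 0.20/3000) = 0.007 in the last.

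**The case against.** On safety, Section 12.3 sets a period for collecting and grading events. It does not require a draw on or after day 28. The Day 85 window also runs to day 42, Section 9.7 lets physicians order further tests, and known abnormalities are followed until they resolve. The full 14-day shortfall needs a visit on the first permitted day. All of this stands: the gap is allowed, not likely. It does not remove the mismatch between the two passages.

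On antibody, all arms share the same windows and the staff are blinded, so timing adds noise and not bias between arms. The power table supports this. Nothing bars an analysis by actual day, and Sections 9.5.1 and 9.6.1 allow kinetics to be explored. That is true, but it is optional and names no method, while duration is a stated objective.

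Three stronger readings are tempting and are not supported:

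- Overlapping windows cause the blur. The Day 113 and Day 141 windows do overlap, on days 56 to 70, but Day 113 has no ELISA or SMFA. The antibody windows do not overlap; the last two only touch, at day 308. The cause is width.
- A 3.65-fold swing swamps the 2.3-fold difference in Section 14.3.1. The first is an extreme within one person under an assumed half-life, and the second is a difference between groups.
- Every window should be tightened. That is a trade-off in field logistics, and using actual sampling days makes it largely unnecessary.

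**Conclusion.** The point holds in two limited parts.

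First, the Day 85 window and the 28-day laboratory period do not fit together. Up to 14 of the 28 days can pass with no scheduled lab during or after them in a participant who follows the schedule. This rests on the documents alone. A reader might infer that laboratory follow-up will generally stop at day 14; the schedule permits that but does not make it the expected course.

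Second, the plan names duration as a secondary objective and has no analysis that estimates it. The sample labelled 84 days may come from anywhere in a twofold range of elapsed time. For half-lives of 30 to 180 days the timing effect within one person is 3.65- to 1.24-fold. These half-lives, first-order decay and even spread over the window are assumptions. The power figures also borrow post-dose-2 inputs from the AS01 trial. On those terms the planned arm-versus-control tests are little affected: at 0.05 power falls from about 0.91 to 0.88 at a 30-day half-life, with no visible loss at 60 days or more. At 0.05/3 it falls from 0.82 to 0.76 at 30 days and by 0.03 or less at 60 and 120 days. What suffers is titre at a given time, the decay rate, and any statement about how long the response lasts.

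**What to change.** 1. Reconcile the Study Day 85 window in Appendix A with the 28-day laboratory period in Section 12.3. Which passage changes is for the sponsor to decide. In the safety report, give the actual day of each participant's last safety lab after dose 3, so that coverage is visible.

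2. Keep the Wilcoxon tests for the arm comparisons. Add to Section 14.3.1 a repeated-measures model of log ELISA on actual days since dose 3, using Days 71, 141, 225, 337 and 393 and keeping out-of-window samples. Report by arm, with confidence intervals, the decay rate or the time above a level named in advance. Report SMFA by actual day as well.

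3. State the shape of decay in advance. Day 71 lies close to the peak and the other samples do not, so a single straight line on the log scale may not fit. Say how samples missed because of phone visits at Days 337 and 393 are treated.

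The cost is a schedule or wording change, a paragraph in Section 14.3 and the use of recorded draw dates. No visit or blood volume is added. The downside is some extra analysis and dependence on the assumed decay shape, with 20 participants per arm to check it.

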Appendix B. Toxicity Tables

Local Reactogenicity Grading¹

Local Reaction to Injectable Product	Mild (Grade 1)	Moderate (Grade 2)	Severe (Grade 3)	Potentially Life Threatening (Grade 4)	
Pain at site	Does not interfere with activity	Repeated use of non-narcotic pain reliever > 24 hours or interferes with activity	Any use of narcotic pain reliever or prevents daily activity	ER visit or hospitalization	
Erythema/Redness at site ²	2.5 – 5 cm	5.1 – 10 cm	> 10 cm	Necrosis or exfoliative dermatitis	
Induration/Swelling at site ³	2.5 – 5 cm and does not interfere with activity	5.1 - 10 cm or interferes with activity	> 10 cm or prevents daily activity	Necrosis	
Bruising at site ²	2.5 – 5 cm	5.1 – 10 cm	> 10 cm	Necrosis or exfoliative dermatitis	
Pruritus at site	Does not interfere with activity	Repeated use of medication > 24 hours or interferes with activity	Prevents daily activity	ER visit or hospitalization	
Limitation of arm movement	Does not interfere with activity	Repeated use of medication > 24 hours or interferes with activity	Prevents daily activity	ER visit or hospitalization	

Abbreviations: ER, emergency room.

¹ The definitions provided in the table are modified versions taken from the FDA Guidance for Industry "Toxicity Grading Scale for Healthy Adults and Adolescent Volunteers Enrolled in Preventive Vaccine Clinical Trials" dated September 2007 and DAIDS Table for Grading the Severity of Adult and Pediatric Adverse Events version 2.1 July 2017.

² In addition to grading the measured local reaction at the greatest single diameter, the measurement should be recorded as a continuous variable.

³ Induration/Swelling should be evaluated and graded using the functional scale as well as the actual measurement.

Vital Sign AE Grading¹

Vital Signs ²	Mild (Grade 1)	Moderate (Grade 2)	Severe (Grade 3)	Potentially Life Threatening (Grade 4)
Fever ³ (°C)	38.0 – 38.4 100.4 – 101.1	38.5 – 38.9 101.2 – 102.0	39.0 – 40 102.1 – 104	> 40 > 104
(°F)	100.4 – 101.1	101.2 – 102.0	102.1 – 104	
Tachycardia - beats per minute; at rest + calm	101 – 115	116 – 130	> 130	ER visit or hospitalization for arrhythmia
Bradycardia - beats per minute ⁴ ; at rest + calm	50 – 54	45 – 49	< 45	ER visit or hospitalization for arrhythmia
Hypertension (systolic) - mm Hg; at rest + calm	141 – 150	151 – 155	> 155	ER visit or hospitalization for malignant hypertension
Hypertension (diastolic) -mm Hg; at rest + calm	91 – 95	96 – 100	> 100	ER visit or hospitalization for malignant hypertension
Hypotension (systolic) - mm Hg; at rest + calm	85 – 89	80 – 84	< 80	ER visit or hospitalization for hypotensive shock

Abbreviations: ER, emergency room.

¹ The definitions provided in the table are taken from the FDA Guidance for Industry "Toxicity Grading Scale for Healthy Adults and Adolescent Volunteers Enrolled in Preventive Vaccine Clinical Trials" dated September 2007.

² Subject should be at rest for all vital sign measurements.

³ Oral temperature; no recent hot or cold beverages or smoking.

⁴ When resting heart rate is between 60 – 100 beats per minute. Use clinical judgment when characterizing bradycardia among some healthy subject populations, for example, conditioned athletes.

Systemic AE Grading¹

Systemic AEs	Mild (Grade 1)	Moderate (Grade 2)	Severe (Grade 3)	Potentially Life Threatening (Grade 4)
Fever (°C)	38.0 – 38.4	38.5 – 38.9	39.0 – 40	> 40
(°F)	100.4 - 101.1	101.2 - 102.0	102.1 – 104	> 104
Headache	No interference with activity	Repeated use of non-narcoti c pain reliever > 24 hours or some interference with activity	Significant; any use of narcotic pain reliever or prevents daily activity	ER visit or hospitalization
Nausea/ Vomiting	No interference with activity or 1 – 2 episodes/24 hours	Some interference with activity or > 2 episodes/24 hours	Prevents daily activity, requires outpatient IV hydration	ER visit or hospitalization for hypotensive shock
Diarrhea	2 – 3 loose stools or < 400 gms/24 hours	4 – 5 stools or 400 – 800 gms/24 Hours	6 or more watery stools or > 800 gms/24 hours or requires outpatient IV hydration	ER visit or hospitalization
Abdominal Pain	No interference with activity	Some interference with activity	Significant; prevents daily activity	ER visit or hospitalization
Fatigue	No interference with activity	Some interference with activity	Significant; prevents daily activity	ER visit or hospitalization
Malaise	No interference with activity	Some interference with activity	Significant; prevents daily activity	ER visit or hospitalization
Myalgia	No interference with activity	Some interference with activity	Significant; prevents daily activity	ER visit or hospitalization
Arthralgia	No interference with activity	Some interference with activity	Significant; prevents daily activity	ER visit or hospitalization
Urticaria	No interference with activity	Requiring PO or topical treatment > 24 hours or IV medications or steroids for ≤24 hours	Requiring IV medication or steroids for >24 hours	ER visit or hospitalization

Abbreviations: ER, emergency room; IV, intravenous; PO, "per os" or oral administration.

¹ The definitions provided in the table are modified versions taken from the FDA Guidance for Industry "Toxicity Grading Scale for Healthy Adults and Adolescent Volunteers Enrolled in Preventive Vaccine Clinical Trials" dated September 2007 and DAIDS Table for Grading the Severity of Adult and Pediatric Adverse Events version 2.1 July 2017.

Mali Laboratory AE Grading: Adults

Hematology and Biochemistry Values ^{1, 2}	Mild (Grade 1)	Moderate (Grade 2)	Severe (Grade 3)	Potentially Life Threatening (Grade 4)
Hemoglobin (Male) - gm/dL	9.5 - 10.3	8.0 - 9.4	6.5 - 7.9	< 6.5 and/or requiring transfusion
Hemoglobin (Female) - gm/dL	8.0 - 9.3	7.0 - 7.9	6.0 – 6.9	< 6 and/or requiring transfusion
WBC Increase - 10 ³ /μL	11.5 – 15.0	15.1 - 20.0	20.1 – 25.0	> 25.0
WBC Decrease - 10³/μL	2.5 - 3.3	1.5 - 2.4	1.0 - 1.4	< 1.0 with fever
Neutrophil/Granulocyte Decrease ³ - 10 ³ /μL	0.80 - 0.90	0.50 – 0.79	< 0.50	< 0.50 with fever
Platelets Decreased - 10 ³ /μL	100 – 110	70 – 99	25 – 69	< 25
Creatinine (Male) - µmol/L	130.00 – 150.99	151.00 – 176.99	177.00 – 221.00	> 221.00 and requires dialysis
Creatinine (Female) - µmol/L	110.00 – 132.99	133.00 – 159.99	160.00 – 215.99	> 216.00 and requires dialysis
Liver Function Tests/ALT - U/L	75.0 – 150.9	151.0 – 300.9	301.0 - 600.0	> 600.0

Abbreviations: ALT, alanine transaminase; WBC, white blood cell.

¹ The laboratory values provided in the tables serve as guidelines and are dependent upon institutional normal parameters. Institutional normal reference ranges should be provided to demonstrate that they are appropriate.

² The clinical signs or symptoms associated with laboratory abnormalities might result in characterization of the laboratory abnormalities as Potentially Life Threatening (Grade 4). For example, a low sodium value that falls within a grade 3 parameter should be recorded as a grade 4 hyponatremia event if the subject had a new seizure associated with the low sodium value.

³ Note, neutropenias are graded and followed, but based on previous experience in African populations, should be interpreted with caution since lower values are more frequently observed in people of African descent (Bain 1996, Haddy, Rana et al. 1999).

